Appendix 1. Study Visit Definition for Psoriasis Symptoms Scale (PSS)

Psoriasis Symptoms Scale (PSS) is collected as a daily diary, entries will be mapped to study week by the following:

Week ^a	Start Day ^b	End Day
Baseline	Date of First Injection ^c - 7	Date of First Injection-1
Week 1	Max(Date of First Injection, Week 2 Assessment Date - 14)	Week 2 Assessment Date - 8
Week 2	Max(Baseline Assessment Date, Week 2 Assessment Date - 7)	Week 2 Assessment Date - 1
Week 3	Max(Week 2 Assessment Date, Week 4 Assessment Date - 14)	Week 4 Assessment Date -8
Week 4	Max(Week 2 Assessment Date, Week 4 Assessment Date - 7)	Week 4 Assessment Date - 1
Week 5	Max(Week 4 Assessment Date, Week 8 Assessment Date - 28)	Week 8 Assessment Date -22
Week 6	Max(Week 4 Assessment Date, Week 8 Assessment Date - 21)	Week 8 Assessment Date -15
Week 7	Max(Week 4 Assessment Date, Week 8 Assessment Date - 14)	Week 8 Assessment Date -8
Week 8	Max(Week 4 Assessment Date, Week 8 Assessment Date - 7)	Week 8 Assessment Date - 1
Week 9	Max(Week 8 Assessment Date, Week 12 Assessment Date - 28)	Week 12 Assessment Date -22
Week 10	Max(Week 8 Assessment Date, Week 12 Assessment Date - 21)	Week 12 Assessment Date -15
Week 11	Max(Week 8 Assessment Date, Week 12 Assessment Date - 14)	Week 12 Assessment Date -8
Week 12	Max(Week 8 Assessment Date, Week 12 Assessment Date - 7)	Week 12 Assessment Date - 1
Week 13	Max(Week 12 Assessment Date, Week 16 Assessment Date - 28)	Week 16 Assessment Date -22
Week 14	Max(Week 12 Assessment Date, Week 16 Assessment Date - 21)	Week 16 Assessment Date -15
Week 15	Max(Week 12 Assessment Date, Week 16 Assessment Date - 14)	Week 16 Assessment Date -8
Week 16	Max(Week 12 Assessment Date, Week 16 Assessment Date - 7)	Week 16 Assessment Date - 1

^a If End Day < Start Day, do not assign specified visit week

^b Assessment Date is the date of the specified visit week's PASI assessment. If the PASI assessment date is missing, the first date from the following order will be selected: (1) date of dosing if injection was given, (2) office visit date if available, or (3) schedule date of visit from the protocol for that visit.

^c If date of first injection is missing, the randomization date will be used.

If multiple PSS assessments on a single day are present, use the latest assessment. If more than 7 days is available between assessment dates, use only the last 7 days as the range. If the range contains at least 4 nonmissing daily assessments, calculate the average for the nonmissing daily assessments to get the weekly score. If range contains fewer than 4 nonmissing daily assessments, then the weekly result is missing.

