### 4.1. Section 2: Schedule of Activities

Section 2: Schedule of Activities

Procedure a	Screening Period	Baseline	Induction Period							Maintenance Period								
			V3	V4	V5	V6	V7	V8	V9	V 10	V 11	V 12	V 13	V 14	V 15	V 16	V 17	V 18
Visit Number	V1 b	V2	V3	V4	V5	V6	V7	V8	V9	V 10	V 11	V 12	V 13	V 14	V 15	V 16	V 17	V 18
Week	-4	0	1	2	3	4	8	12	16	20	24	28	32	36	40	44	48	52
Day with Visit Tolerance Interval	≤28 days from V2	1	8 ± 3	15 ± 3	22 ± 3	29 ± 3	57 ± 5	85 ± 5	113 ± 5	141 ± 5	169 ± 5	197 ± 5	225 ± 5	253 ± 5	281 ± 5	309 ± 5	337 ± 5	365 ± 5
Chest Radiography for TB Screening e	X e																	X
Investigator Completed Clinical Efficacy Scales																		
Assessment of dermal symptoms		X		X		X	X	X	X	X	X	X	X	X	X	X	X	X
Global improvement score				X		X	X	X	X	X	X	X	X	X	X	X	X	X
Laboratory Tests																		
HBV DNA testing n	X					X	X	X	X	X	X	X	X	X	X		X	
Beta-D-glucan*	X																	
KL-6**	X																	

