6.3.1. Nonresponder Imputation

The nonresponder imputation (NRI) method can be justified based on the composite strategy (ICH E9R1) for handling intercurrent events. In this strategy patients are defined as responders only if they meet the clinical requirements for response at the predefined time AND they remain on the assigned study treatment. Failing either criteria by definition makes them nonresponders.

Analysis of binary categorical efficacy and health outcome variables will be assessed using an NRI method. Patients will be considered nonresponders for the NRI analysis if they do not meet the clinical response criteria or have missing clinical response data at the analysis time point. Randomized patients without at least 1 postbaseline observation will also be defined as nonresponders for the NRI analysis.

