BSA	Proportion of patients with $\leq 1\%$ of BSA with psoriasis involvement	CMH analysis with NRI	ITT	All scheduled visits in Induction Period; All scheduled visits in Induction and Maintenance Periods
	BSA change from baseline	MMRM; ANCOVA with mBOCF	ITT	All scheduled visits in Induction Period; All scheduled visits in Induction and Maintenance Periods
PSS	PSS Symptoms Score of 0; PSS Signs Score of 0	CMH analysis with NRI	ITT - Patients with Baseline PSS Symptoms Score ≥ 1 and PSS Signs Score ≥ 1 , respectively	All scheduled weeks in Induction Period; All scheduled weeks/visits in Induction and Maintenance Periods
	Change from baseline for PSS Symptoms Score, Signs Score, and Item Scores	MMRM; ANCOVA with mBOCF	ITT	All scheduled weeks in Induction Period; All scheduled weeks/visits in Induction and Maintenance Periods
PSSI	PSSI change from baseline	MMRM; ANCOVA with mBOCF	ITT - Patients with Scalp Involvement at Baseline	All scheduled visits in Induction Period; All scheduled visits in Induction and Maintenance Periods
	PSSI score = 0	CMH analysis with NRI	ITT - Patients with Scalp Involvement at Baseline	All scheduled visits in Induction Period; All scheduled visits in Induction and Maintenance Periods
PPASI	PPASI change from baseline	MMRM; ANCOVA with mBOCF	ITT - Patients with Palmoplantar Involvement at Baseline	All scheduled visits in Induction Period; All scheduled visits in Induction and Maintenance Periods
	PPASI 50; PPASI 75; PPASI 100;	CMH analysis with NRI	ITT - Patients with Palmoplantar Involvement at Baseline	All scheduled visits in Induction Period; All scheduled visits in Induction and Maintenance Periods
NAPSI	NAPSI change from baseline	MMRM; ANCOVA with mBOCF	ITT - Patients with Nail Psoriasis Involvement at Baseline	All scheduled visits in Induction Period; All scheduled visits in Induction and Maintenance Periods

Description of Efficacy/Health Outcomes Analyses

Measure	Variable	Analysis Method (Section 6.1.2)	Population (Section 6.1.1)	Time Point and Period
NAPSI	NAPSI score = 0	CMH analysis with NRI	ITT - Patients with Nail Psoriasis Involvement at Baseline	All scheduled visits in Induction Period; All scheduled visits in Induction and Maintenance Periods
DLQI	DLQI (0,1) and ≥ 5 -point reduction from baseline	CMH analysis with NRI	ITT - Patients with Baseline DLQI ≥ 5	All scheduled visits in Induction Period; All scheduled visits in Induction and Maintenance Periods

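### Appendix 1 counts PSS diary weeks back from the next visit, so visits close together within tolerance can turn a complete Week 3 or Week 5 diary (and Week 9 or 13, if diaries run that long) into nonresponse in supportive analyses

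*SAP*

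**What the plan says.** SAP Appendix 1 maps daily PSS entries to study weeks by date. Each window is counted back from the next visit's assessment date (normally the PASI date) and may not start before the previous visit. Week 3 runs from "Max(Week 2 Assessment Date, Week 4 Assessment Date - 14") to "Week 4 Assessment Date -8". Week 5 starts at "Max(Week 4 Assessment Date, Week 8 Assessment Date - 28") and ends 22 days before the Week 8 date. Weeks 9 and 13 repeat the Week 5 pattern one and two visits later.

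Two rules deal with short windows. Footnote a says "If End Day < Start Day, do not assign specified visit week". The closing text says "If range contains fewer than 4 nonmissing daily assessments, then the weekly result is missing".

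Table AMAJ.6.6 analyses PSS Symptoms Score 0 and Signs Score 0 by CMH with NRI at "All scheduled weeks in Induction Period". SAP section 6.3.1 defines the imputation: "Patients will be considered nonresponders for the NRI analysis if they do not meet the clinical response criteria or have missing clinical response data". Nothing exempts a week that is short or empty only because of when the visits took place.

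The row "Day with Visit Tolerance Interval" in the addendum's Schedule of Activities allows 3 days either way at Weeks 2 and 4, and 5 days either way at Weeks 8, 12 and 16.

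**The concern.** On the planned days every window holds 7 days. When two visits move towards each other, the whole shortfall falls on the first week after the earlier visit, because that week is the one cut off. A patient who attends within tolerance, completes every entry and has no symptoms can then be scored as a nonresponder for that week. The loss falls only on particular weeks, so the by-week PSS response curves would dip there because of visit scheduling, not because of symptoms.

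**Working it through.** **Inputs.** Window formulas, footnote a and the 4-day minimum: SAP Appendix 1. Visit days 15 ± 3, 29 ± 3, 57 ± 5, 85 ± 5 and 113 ± 5: Schedule of Activities in the Japan addendum. The main protocol was not available, so its visit windows are assumed to be the same.

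**Window length.** Let D be the number of days between the two bounding visits. Length = end day − start day + 1, floored at 0.

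- Week 3: min(7, D − 7)
- Weeks 5, 9 and 13: min(7, D − 21)

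**Planned schedule.** D = 14 gives min(7, 7) = 7. D = 28 gives min(7, 7) = 7. All 16 weeks have 7 days, which matches the up-to-7-day basis in Table AMAJ.6.5.

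**Within tolerance.**

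| Week | Smallest D | Days left at smallest D | Fewer than 4 days when | No days when |
|---|---|---|---|---|
| 3 | 26 − 18 = 8 | 1 | D ≤ 10 | not reached |
| 5 | 52 − 32 = 20 | 0 | D ≤ 24 | D ≤ 21 |
| 9 | 80 − 62 = 18 | 0 | D ≤ 24 | D ≤ 21 |
| 13 | 108 − 90 = 18 | 0 | D ≤ 24 | D ≤ 21 |

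In each row the threshold is 4 days short of plan (14 − 4 = 10; 28 − 4 = 24).

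The other weeks never fall below 4 days within tolerance. The minimum is 4 at Weeks 1, 10 and 14, 6 at Week 6, and 7 at Weeks 2, 4, 7, 8, 11, 12, 15 and 16. Appendix 1's instruction to use only the last 7 days does not help, because no window is longer than 7 days.

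**Share of allowed visit-day pairs that are at least 4 days short.**

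- Week 3: (3 + 2 + 1)/(7 × 7) = 6/49 = 12%
- Week 5: (1 + 2 + 3 + 4 + 5)/(7 × 11) = 15/77 = 19%
- Weeks 9 and 13: (7 + 6 + 5 + 4 + 3 + 2 + 1)/(11 × 11) = 28/121 = 23% each

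These are frequencies only if visit days are independent and uniform over the tolerance. With deviations assumed normal, truncated at the tolerance, and diaries complete:

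| Assumed SD of visit day | Week 3 | Week 5 | Weeks 9 and 13 |
|---|---|---|---|
| 1 day | about 1% | about 1% | about 1% |
| 1.5 days | 4% | 4.5% | 5% |
| 2 days | 7% | 9% | 10% |
| uniform (upper case) | 12% | 19% | 23% |

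**Effect on the estimate.** If a share m of patients is lost this way, unrelated to arm or response, each response rate is multiplied by 1 − m, and so is the risk difference. At m = 0.01 it keeps 99% of its size; at m = 0.23, 77%.

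**The case against.** The case for treating this as small is strong, and most of it stands.

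- **Status of the weeks.** Table AMAJ.4.1 lists PSS once, as Symptoms Score 0 at Week 16. The other weeks enter only through Table AMAJ.6.6, as supportive results outside the graphical testing scheme. A reader might infer that the Week 16 major secondary endpoint is damaged. It is not: its Appendix 1 window has 7 days at every allowed visit gap.
- **Weeks 9 and 13.** Table AMAJ.6.5 has diaries only up to Visit 7 (Week 8) and office collection after that, while Appendix 1 maps diary days through Week 16. The largest figures therefore depend on which text governs. Weeks 3 and 5 are affected on either reading.
- **Size.** It is tempting to quote 23% as the expected loss. The documents give no visit-date distribution, and the uniform case makes the edge of the tolerance as likely as the target day. On the other side, SAP section 6.1 keeps assessments made outside the windows, so some gaps could be shorter than those enumerated.
- **Direction.** A reader might infer bias in favour of one arm. The rule is the same in every arm and visits are blinded, so there is no evident reason for the loss to differ. The expected effect is attenuation, not a false benefit.
- **Reach.** Not every PSS analysis is hit. In MMRM the week is simply missing, and with mBOCF the last value is carried forward.
- **Unassigned weeks.** Footnote a does not say whether an unassigned week is left out or imputed. Counting it as nonresponse follows from section 6.3.1, but that is an inference. Weeks left with 1 to 3 days do not depend on it, because Appendix 1 makes them missing outright.

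None of this removes the mechanism: as written, the rules can turn a complete diary into nonresponse.

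**Conclusion.** The point holds for supportive by-week response rates. Appendix 1, the 4-day minimum and NRI together can score a fully adherent patient as a nonresponder for PSS Symptoms 0 or Signs 0 at Weeks 3 and 5, and at Weeks 9 and 13 if diaries continue past Visit 7. Rates at those weeks are biased downward and treatment differences are attenuated.

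The plausible loss with complete diaries is wide, from about 1% to the upper case in the last row of the table. It rests on an assumed visit spread, on independent visit dates, and on the main protocol sharing the addendum's tolerances. The actual visit dates, which can be examined without treatment codes, would settle where in that range the trial lies.

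**What to change.** **Change to Appendix 1.** For Weeks 3, 5, 9 and 13 only, keep the start day and set the end day to the later of the current end day and start day + 6. The window is then always 7 days and still closes before the next visit. When the gap is at or above plan, nothing changes. Leave Week 1 and all other weeks as they are. Reconcile Table AMAJ.6.5 with Appendix 1 on when diary collection stops; if it stops at Visit 7, only Weeks 3 and 5 need the change.

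**Cost.** Up to four rows of text and a small programming change, best made before the study team is unblinded. The statistical price is overlap. In every rescued case 4 to 7 diary days are shared with the following week: 14 − D for Week 3 (4 days at D = 10, 6 at D = 8) and, down to D = 21, 28 − D for the others (4 days at D = 24, all 7 at D = 21). At D = 18 to 20 the following week lies wholly inside the rescued one, and 1 to 3 days are also shared with the week after that. The rescued value therefore largely repeats its neighbour.

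**Alternative.** If the sponsor does not accept that overlap, state that a week cut below 4 days or left unassigned only because of visit timing is left out of NRI for that week. The cost is a denominator that varies by week. This would also settle what footnote a leaves open.

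**What not to do.** Counting all windows forward from the previous visit moves the shortage to the visit weeks: as few as 1 day at Week 4 and none at Weeks 8, 12 and 16, which would harm the Week 16 endpoint. Fixed 7-day weeks from first injection leave only 4 days before the earliest allowed visit at Weeks 2 and 4, and 2 days at Weeks 8, 12 and 16.

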Appendix 2. Analysis Plan for Japan Addendum

App.2.1. Japan Addendum Design and Objectives

The main protocol for Study I6T-MC-AMAJ (AMAJ) enrolls patients with plaque psoriasis (Cohort 1). In parallel, the AMAJ(1) addendum will enroll Japanese patients who are diagnosed as generalized pustular psoriasis (GPP) by the Japanese Dermatological Association or erythrodermic psoriasis (EP) who have $\geq 80\%$ body surface area (BSA) involvement (with inflammatory erythema) (Cohort 2). Approximately 8 patients with GPP and 8 patients with EP will be enrolled in Cohort 2 in Japan. During the Induction Period, GPP and EP patients will receive 250-mg mirikizumab subcutaneously (SC) at Weeks 0, 4, 8, and 12. During the Maintenance Period, starting at Week 16, GPP and EP patients will receive 250-mg mirikizumab every 8 weeks (Q8W) SC for up to a total of 52 weeks. Placebo control is not required for the GPP and EP patient arms because placebo-controlled studies are not ethical for patients with these severe conditions. The enrollment period of Cohort 2 will begin in parallel with the enrollment period of Cohort 1, but Cohort 2 enrollment may continue for a longer period of time if necessary to achieve the numbers planned for Cohort 2.

Eight patients with GPP and 8 patients with EP will be enrolled in Cohort 2 in Japan. The number of patients with GPP and EP is based on the population size of these patients being very small in Japan (Umezawa et al. 2003, Rosenbach et al. 2010).

Objectives in the main protocol are not applied to GPP and EP patients. Selected endpoints in the main protocol are applied to GPP and EP patients. [Table AMAJ.App.1](#) shows the addendum objectives and endpoints which are added to the study as exploratory objectives:

Table AMAJ.App.1. Japan Addendum Objectives and Endpoints

Exploratory To assess the efficacy of mirikizumab in patients with GPP
	
GPP ONLY Time course of response to treatment as measured by the following measures:
 
 • global improvement score • assessment of dermal symptoms for GPP* • change from baseline in PASI • change from baseline in DLQI total score 
At Week 16 and Week 52:
 
 • change from baseline in global improvement score** • change from baseline in assessment of dermal symptoms for GPP • change from baseline in PASI • change from baseline in DLQI total score

To assess the efficacy of mirikizumab in patients with EP
	
EP ONLY Time course of response to treatment as measured by the following measures:
 
 • global improvement score • change from baseline in PASI • change from baseline in DLQI total score 
At Week 16 and Week 52:
 
 • global improvement score • change from baseline in PASI • change from baseline in DLQI total score

Abbreviations: DLQI = Dermatology Life Quality Index; GPP = generalized pustular psoriasis; EP = erythrodermic psoriasis; PASI = Psoriasis Area and Severity Index.

* This endpoint is written as it is in Japan Addenda (1.1), but should be updated to “change from baseline in assessment of dermal symptoms for GPP”.

** This endpoint is written as it is in Japan Addenda (1.1), but should be updated to “global improvement score”.

App.2.2. Japan Addendum General Considerations

The benefit/risk profile to support global registrations will be based on the analysis of Cohort 1.

Patients enrolled in Cohort 2 will not be included in the analysis supporting global registrations. To support registration in Japan, efficacy, health outcome, and safety analysis for plaque psoriasis, GPP, and EP will be conducted separately.

The Japan Addendum Intent-to-Treat (ITT) Population – Patients with GPP or EP is defined as all GPP and EP patients who enrolled in the Japan addendum, even if the patient does not take the assigned treatment, does not receive the correct treatment, or otherwise does not follow the protocol. All patients are assigned to mirikizumab treatment. Efficacy/Health outcome analyses for the combined Induction and Maintenance Periods will be conducted on this population. Generalized pustular psoriasis and EP patients will be reported separately.

The Japan Addendum Safety Population – Patients with GPP or EP is defined as all GPP and EP patients who enrolled in the Japan addendum and received at least 1 dose of study treatment. Safety analyses for the combined Induction and Maintenance Periods (which are similar to the All Active Treatment Periods for the 250-mg mirikizumab Q4W/250-mg mirikizumab Q8W in the main SAP) will be conducted on this population. Generalized pustular psoriasis and EP patients will be reported separately.

The definitions of the baselines for efficacy, health outcomes, and safety analyses in the Japan Addendum are the same as in the main protocol/SAP.

Due to small sample size in the Japan Addendum, no formal inferential statistics will be performed. Data will be summarized for GPP and EP patients separately. The methods of summary are the same as in the main SAP

The following general summaries and/or listings will be provided based on Japan Addendum ITT Population – Patients with GPP or EP:

- patient disposition including treatment disposition and study disposition
- patient demographics and other baseline characteristics
 - Add baseline GPP dermal symptom total score
- preexisting conditions
- prespecified medical history
- previous psoriasis therapy and the corresponding reason for discontinuation
- prior medications and concomitant medications
- study treatment exposure
- listing of randomization/treatment assignment
- important protocol deviations
- treatment compliance

App.2.3. Japan Addendum Efficacy/Health Outcome Analyses

[Table AMAJ.App.3](#) includes the description and derivation of the additional efficacy measures and endpoints that are collected in the Japan Addendum

[Table AMAJ.App.4](#) provides the detailed analyses for efficacy/health outcomes analyses in the Japan Addendum.

Table AMAJ.App.3. Description and Derivation of Additional Efficacy/Health Outcomes Measures and Endpoints for Japan Addendum

Measure	Description	Variable	Derivation/Comment	Imputation Approach if with Missing Components
Global Improvement Score	
 Collected for patients with GPP or EP from Week 2. Assessed in the 4 grades by comparing the psoriatic findings: (1) resolved, (2) improved, (3) unchanged, (4) worsened. Assessed based on the comparison of the psoriatic findings, sPGA, PASI score, and other evaluations with those at the baseline. 	Global improvement score	As collected	Single item, missing if missing
Assessment of dermal symptoms	
 According to the Japanese Dermatological Association GPP revised criteria.^a Performed only for patients with GPP. Skin symptoms are assessed by the score with the area of erythema (on a 0-3 scale), the area of erythema with pustules (on a 0-3 scale), and the area of skin edema (on a 0-3), where 0 = none; 1 = mild; 2 = moderate; 3 = severe. 	GPP dermal symptom total score	Sum of scores of the area of erythema, the area of erythema with pustules, and the area of skin edema. Range from 0-9.	If any individual score is missing, the total score will not be calculated, hence missing

Abbreviations: EP = erythrodermic psoriasis; GPP = generalized pustular psoriasis; PASI = Psoriasis Area and Severity Index; sPGA = static Physician's Global Assessment.

^a (Terui et al. [WWW]).

Table AMAJ.App.4. Description of Efficacy/Health Outcomes Analyses for Japan Addendum

Measure	Variable	Analysis Method	Population	Time Point and Period
Global Improvement Score	Global improvement score	Descriptive statistics for each grade based on observed	Japan Addendum Intent-to-Treat Population – Patients with GPP or EP	All scheduled visits in Induction and Maintenance Periods
GPP dermal symptom total score	GPP dermal symptom total score change from baseline	Descriptive statistics based on observed and mBOCF	Japan Addendum Intent-to-Treat Population – Patients with GPP	All scheduled visits in Induction and Maintenance Periods
PASI	PASI change from baseline	Descriptive statistics based on observed and mBOCF	Japan Addendum Intent-to-Treat Population – Patients with GPP or EP	All scheduled visits in Induction and Maintenance Periods
DLQI	DLQI total score change from baseline	Descriptive statistics based on observed and mBOCF	Japan Addendum Intent-to-Treat Population – Patients with GPP or EP	All scheduled visits in Induction and Maintenance Periods

Abbreviations: DLQI = Dermatology Life Quality Index; EP = erythrodermic psoriasis; GPP = generalized pustular psoriasis; mBOCF = modified baseline observation carried forward; PASI = Psoriasis Area and Severity Index.

App.2.4. Japan Addendum Safety Analyses

The following safety summaries will be provided for the Japan Addendum Safety Population – Patients with GPP or EP, for the Induction and Maintenance Periods:

- overview of adverse events (AEs)
- treatment-emergent adverse event (TEAE) by Preferred Terms (PTs)
- TEAE by PTs within System Organ Class
- TEAE maximum severity by PTs
- serious adverse event (SAE) by PTs
- AEs leading to treatment discontinuation
- listings of SAEs
- laboratory tests: box plot of change from baseline by visit
- vital signs: box plot of change from baseline by visit
- immunogenicity: incidence of antidrug antibodies

References

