- s If a patient discontinues IP early, the patient will complete the ETV and then enter the Post-Treatment Follow-up Period (V801 + V802).
- t All patients who receive IP but do not participate in Study I6T-MC-AMAH must enter the Follow-up Period and complete V801 + V802.
- \* Beta-D-glucan is required at screening and, if an investigator believes it is warranted, at subsequent visits; a beta-D-glucan test may be included in the work up panel at any time during the study, including in the follow-up period. If the beta-D-glucan test is positive, PCP needs to be ruled out. If PCP is ruled out and the investigator deems the patient fit to continue, the patient may continue in the study. If a patient has a confirmed diagnosis of PCP during the study, the patient must discontinue the study.

\*\* KL-6 is required at screening and, if an investigator believes it is warranted, at subsequent visits; a KL-6 test may be included in the work-up panel at any time during the study, including in the follow-up period.

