#### 10.3.1. General Statistical Considerations

The benefit/risk profile to support global registrations will be based on the analysis of Cohort 1.

Patients enrolled in Cohort 2 will not be included in the analysis supporting global registrations. To support registration in Japan, efficacy and safety analysis for plaque psoriasis, GPP, and EP

will be conducted separately. Safety data for all patients (plaque psoriasis, GPP, EP) will also be assessed.

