6.1.1.1. Study Time Intervals

[Table AMAJ.6.3](#) displays a list of study periods along with the definition of which patients will be considered to have entered the study period and when the individuals start and end the study period. The table shows both a date and a time.

To calculate the length of any time interval or time period in this study the following formula will be used:

$$\text{Length of interval (days)} = \text{End Date} - \text{Interval Start Date} + 1$$

Only for the purpose of calculating the length of study period time intervals, the words “prior to” in [Table AMAJ.6.3](#) should be understood to mean “the day before” while the words “after” should be understood to mean “the day after.”

To convert any time length from days to years, the following formula will be used:

$$\text{Length of interval (years)} = \text{Length of interval (days)} / 365.25$$

To convert any time length from days to weeks, the following formula will be used:

$$\text{Length of interval (weeks)} = \text{Length of interval (days)} / 7$$

Table AMAJ.6.3. Definition of Study Period Time Intervals

Study Period	Start Definition	End Definition
Screening: All patients who sign informed consent are considered as entering the Screening Period.	Informed consent date	Prior to the start of induction
Induction Period: All patients who are randomized to the study are considered as entering the Induction Period.	At the first injection following randomization date/time ^a . For patients who are randomized but not dosed, the Induction Period starts on the date of randomization.	Prior to the start of maintenance. For patients who discontinue before or on the Week 16 visit, the induction period ends at the last date of treatment discontinued date or last treatment visit date.
Maintenance Period: All patients who had any Week 16 to Week 52 visits (except the ones who discontinued the study at Week 16) are considered to have entered the Maintenance Period.	At the Week 16 dosing date/time. ^a If a patient is unable to be dosed at the Week 16 visit, the Maintenance Period starts at the Week 16 visit. If the patient misses the Week 16 visit, the Maintenance Period starts at Day 118.	After the Week 52 visit date. If patients discontinued prior to Week 52, the Maintenance Period ends at the last date of treatment discontinued or last treatment visit date.

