 - For “all miri + follow-up” and “all secu + follow-up”, the All Active Treatment and Follow-Up Periods will be used.

Table AMAJ.6.7. Summary Tables Related to Adverse Events

Analysis	Population
Overview of AEs	I, A
Summary of TEAE PTs by decreasing frequency	I, A
Summary of TEAE PTs occurring in $\geq 1\%$ of patients by decreasing frequency	I, A
Summary of TEAE PTs by decreasing frequency within SOC	I, A
Summary of TEAE PTs by maximum severity by decreasing frequency	I, A
Summary of SAE PTs by decreasing frequency	I, A
Summary of AEs leading to treatment discontinuation	I, A
Listing of SAEs	ITT
Listing of Deaths	All Entered Patients

Abbreviations: A = All Active Treatment Safety; AE = adverse event; I = Induction Safety; ITT = Intent-to-Treat; PT = preferred term; SAE = serious adverse event; SOC = System Organ Class; TEAE = treatment-emergent adverse event.

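### SAP Appendix 2 gives the Cohort 2 (GPP/EP) safety summaries no window covering the 12-week post-treatment follow-up, and leaves the period of the SAE listing unclear

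*SAP*

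**What the plan says.** **Cohort 2 window.** SAP App.2.2 defines the Japan Addendum Safety Population and fixes its period: "Safety analyses for the combined Induction and Maintenance Periods (which are similar to the All Active Treatment Periods" of the main SAP's 250 mg/250 mg mirikizumab arm. App.2.4 repeats the limit in its lead-in, "Patients with GPP or EP, for the Induction and Maintenance Periods". Beneath that lead-in stand the AE overview, the TEAE and SAE summaries, discontinuations due to AEs, "listings of SAEs", the laboratory and vital-sign box plots, and antidrug antibodies.

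**Where the window ends.** In SAP Table AMAJ.6.3 the Maintenance Period closes after the Week 52 visit. For early stoppers the rule is "If patients discontinued prior to Week 52, the Maintenance Period ends at the last date of treatment discontinued or last treatment visit date". Follow-up is its own interval, entered by having Visit 801 or 802, and it begins after the treatment periods end.

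**Who is followed.** Footnote t of the addendum's Schedule of Activities says: "All patients who receive IP but do not participate in Study I6T-MC-AMAH must enter the Follow-up Period and complete V801 + V802". Visit 802 falls 12 weeks after the last study visit.

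**Cohort 1.** SAP Section 6.14.2 sets two post-baseline periods for the All Active Treatment Safety Population. For the second, "the All Active Treatment and Follow-Up Periods will be used". Table AMAJ.6.2 carries matching columns for all mirikizumab and for secukinumab, marked + FUP.

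**The concern.** The plan obliges treated Cohort 2 patients who do not roll over to be seen for a further 12 weeks, and then names a reporting window that stops before those weeks begin. Cohort 1 is reported both with and without follow-up; Cohort 2 is reported only without.

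The patients affected are those who stopped early and those who completed Week 52 but declined the extension. The addendum's rationale describes both conditions as sometimes life-threatening if not adequately treated. It also adds safety monitoring for Japan that extends into follow-up: HBV DNA testing at both follow-up visits for antibody-positive patients, and other tests where the investigator judges them warranted. Events after the last treatment visit are therefore of real interest. In groups of about 8, a single unreported patient changes the picture visibly.

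**Working it through.** The SAP states no figure to reproduce. The check compares period and population definitions, followed by simple arithmetic.

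1. **Is follow-up inside the Cohort 2 window?** No. App.2.2 and App.2.4 both name Induction and Maintenance. Table AMAJ.6.3 ends Maintenance before follow-up starts. App.2.2 likens the window to the All Active Treatment Periods, whereas the main SAP has a separate entry for All Active Treatment plus Follow-up. App.2.2 also says that summary methods are those of the main SAP, but this concerns methods; the period is stated explicitly in both places.

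2. **Do the main SAP's follow-up outputs pick up Cohort 2?** Not by definition. The + FUP columns use the All Active Treatment Safety Population, and the main SAE listing uses ITT (Table AMAJ.6.7). Table AMAJ.6.1 defines both as randomized patients. The addendum's design section assigns GPP and EP patients to mirikizumab without randomization, and App.2.2 gives them their own populations.

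3. **Is the SAE listing restricted?** It stands under the App.2.4 lead-in, so a literal reading restricts it. However, that lead-in speaks of summaries, and in Table AMAJ.6.7 the main SAE listing is tied to a population with no period. The text does not settle the matter.

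4. **What would still be reported?** Table AMAJ.6.7 puts the deaths listing on All Entered Patients, which Table AMAJ.6.1 defines as everyone who signed consent. On that wording it includes Cohort 2.

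5. **Size.** Inputs: 8 GPP and 8 EP patients (addendum Section 10.1) and 12 weeks of follow-up (addendum Section 5.1 and Schedule of Activities). Let *k* be the number of dosed patients who do not enter AMAH and who complete follow-up.
   - Omitted time = 12 × *k* patient-weeks.
   - *k* = 0 gives 0; *k* = 16 gives 12 × 16 = 192 patient-weeks.
   - *k* is not given, so only this range can be stated.
   - For a Week 52 completer who does not enter AMAH, the share of observed time outside the window is 12 / (52 + 12) = 12/64 = 18.75%. It is larger for earlier stoppers.
   - One patient in a group of 8 is 1/8 = 12.5 percentage points. The shift applies to a given row only if that patient is not already counted there for an on-treatment event.

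**The case against.** The case for leaving the plan alone has several parts.

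- **An on-treatment window is defensible.** SAP Section 5.1.4 allows other psoriasis therapy during follow-up, so attributing late events to mirikizumab in an uncontrolled cohort is difficult. The main SAP also reports without follow-up first. This stands as a reason to show follow-up separately. It is not a reason to show nothing, because Cohort 1 faces the same confounding and still has the second window.
- **The consequence is limited.** Cohort 2 is exploratory, has no formal inference and is outside the global registration analyses. The follow-up data are collected through the final database lock, and SAP Section 6.1 permits additional analyses. This stands: the gap is in planned reporting, not in data collection.
- **Other outputs may catch some events.** Section 6.21 counts an SAE for the registry whether or not it is treatment-emergent, and Section 6.20 plans DSUR reports. Neither names Cohort 2 or excludes it. Section 6.16 places the list of Japan-site outputs in a separate document, and the main protocol is not among the documents supplied. The conclusion is therefore limited to the outputs specified in Appendix 2.

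A reader might go further in four ways that the documents do not support.

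- One might infer that follow-up SAEs are certainly excluded from the SAE listing. The wording is ambiguous, as step 3 shows.
- One might infer that the Japan safety picture will look better than the data. That presumes events occur in follow-up, which nobody can know from the plan. What can be said is that widening the window cannot lower the number of patients with an event.
- One might read addendum Section 10.3.1, "Safety data for all patients (plaque psoriasis, GPP, EP) will also be" assessed, as a commitment breached here. That sentence gives no period and concerns assessment across diagnoses, which is a separate matter.
- One might ask for a by-patient listing of follow-up HBV DNA, beta-D-glucan, KL-6 and radiography results. The SAP plans no such listing for Cohort 1, so its absence is not an inconsistency.

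**Conclusion.** The point holds within these limits. App.2.2 and App.2.4 agree with each other and exclude follow-up from the Cohort 2 safety summaries, so applying the SAP as written leaves AEs and SAEs that start in the 12-week follow-up out of every Cohort 2 event summary in Appendix 2. The SAE listing would lose them on a literal reading, but this part is an ambiguity to be resolved rather than a demonstrated exclusion. Deaths should still be listed.

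The omitted observation is 12 weeks per patient not entering AMAH, or 0 to 192 patient-weeks overall. The upper bound assumes 16 dosed patients, none entering AMAH and all completing Visit 802. A single omitted patient with an event is worth 12.5 percentage points in a group of 8, assuming 8 are enrolled and dosed. The correction should be made: it is specific, it follows a rule the SAP already applies to Cohort 1, and it costs little.

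**What to change.** In App.2.2 and App.2.4, keep the Induction and Maintenance summaries as they are. Add a second post-baseline window for Cohort 2, Induction + Maintenance + Follow-up, matching the + FUP window of Section 6.14.2 and Table AMAJ.6.2. Apply it to the AE overview and to the TEAE and SAE summaries, with GPP and EP still reported separately. Add one sentence stating that the Cohort 2 SAE listing covers all periods.

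The cost is a wording change to Appendix 2 and a rerun of existing outputs for about 16 patients, with no new data. Event counts may rise, and follow-up events may be confounded by other psoriasis therapy. The second window should therefore be displayed beside the on-treatment one and not replace it.
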